5. BACKGROUND*

See grant: "RESEARCH STRATEGY" (p.2-4) for details. The Procedures for Phase 2 have been modified from the original submission. Updated Procedures are as follows:

Procedures

Screening, recruitment, eligibility and training procedures are in C.2.1 and the Eligibility criteria document.

Randomization will occur following determination of eligibility using an urn procedure and stratifying on 1) other (than opioid) substance use disorder no/yes, 2) gender/sex, 3) race/ethnicity.

TAU with MyMAT (n = 51). In the acute care setting, the Behavioral Health Service run by Drs. [name] and [name] provides SBIRT for substance use disorders, including OUD. They provide SBIRT as part of TAU, including, when possible, warm handoff contact with outpatient MOUD treatment that includes a scheduled outpatient appointment, optimally within 48 hours of the ED visit. Patients randomized to this group will also receive MyMAT, a mobile application with opioid treatment educational content, as an attention control measure against OARS+CM. TAU outpatient suboxone treatment consists of urine toxicology screening, group/individual therapy, and MOUD prescription continent on drugnegative (except cannabis, which is legal in MA) urine toxicology. Treatment visits are typically, weekly in weeks 1-4 and then taper over time, to every other week in weeks 5-8, and monthly in weeks 9-12 and thereafter. Nonadherence can lead to increased frequency/intensity of therapy and urine toxicology until the patient stabilizes. If increased frequency/intensity is unsuccessful, patients may be referred to detoxification and subsequently re-admitted to outpatient care when appropriate.

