11. PROCEDURES INVOLVED*

Measures: For Phase 1, the System Usability Scale (SUS) (patients and clinicians), Timeline Followback (TLFB) (patients only), and Addiction Severity Index (ASI) (patients only) will be used and is included in this submission. For Phase 2, The Mini Quiz (MQ), Mini-Usability Acceptability Testing (Mini-UAT) questionnaire, Timeline Followback (TLFB), PROMIS Pain Intensity and Interference Scales (PIIS), HIV Risk Behavioral Scale (HRBS), Post-traumatic Stress Diagnostic Scale for DSM-5 (PDS), Treatment Satisfaction Scale (TSS), and the System Usability Scale (SUS) will be used and are included in this submission.

Assessments/Procedures for Phase 2	Intake	Onboarding	Transition to Suboxone	Week 1 to 12	Month 1	Month 3 / End of Tx	Month 6
Mini Quiz, Patient form, OUD	X						
Mini-UAT, Service Utilization, TLFB	X				Х	Х	Х
PIIS, HRBS, PDS, U-Tox	X				Х	Х	Х
Healthcare Utilization	X						Х
App training, warm hand-off scheduling outpatient Suboxone intake		Х					
Monitor completion of MOUD intake			Х				
MOUD TAU / OARS+CM				Х			
Monitor treatment attendance/u-tox				X			
Treatment satisfaction, SUS*						Х	

^{*}Only for OAR+CM group

Phase 1: Aim 1 (Develop OARSCM): 30 Clinicians (20 user testing, 10 dyads) and 30 Patients

- 1a. After the OARSCM is developed, patients meeting criteria and consenting to participate will be guided through using the mobile application on their personal smartphone. If the participant's smartphone is not available for use to complete the instructed tasks, the participant will be able to use a study-provided iPad.
- 1b. Clinicians not associated with a specific patient participant verbally consenting to participate after reviewing the User Testing Fact Sheet will be guided through using the provider portal using a test account on a study provided computer in a private office.
- 1c. Clinicians working at the UMass Bridge Clinic, at the CleanSlate Addiction Treatment Center at SaVida Health, and at Spectrum Health Systems associated with a patient participant (considered a dyad) verbally consenting to participate after reviewing the Dyad Fact Sheet will receive an in-person or virtual training on the provider portal on a study provided computer in a private office. After the training, the clinician will provide standard MAT treatment to patient participants and use the OARSCM provider portal to track treatment.

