25. LOCAL NUMBER OF SUBJECTS

Phase 1 Aim 1 (Develop OARSCM): 30 individuals with OUD and 30 providers/clinicians will be recruited to provide feedback to improve the interface and features.

Phase 2 Aims 1 & 2 (RCT of OARSCM): 102 patients will be enrolled and randomized into OARS+CM (n=51), or TAU with MyMAT (n=51) to determine efficacy of OARSCM. See grant: "RESEARCH STRATEGY" (p12) "Procedures" for further details.

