Phase 2, RCT. will proceed with the intent-to-treat sample. Initial analyses will compare groups on baseline and demographic variables using chi-square test (for categorical variables) and analysis of variance (for continuous variables). Variables that significantly differ between groups or are theoretically important, such as pain and other (non-opioid) substance use disorder will be used as covariates in multivariate analysis, when appropriate. For end-of-treatment outcomes, analysis will compare groups via chi-square, Kruskal-Wallis test, and analysis of variance (ANOVA) or analysis of covariance (ANCOVA) tests, as appropriate. Evaluation of changes in outcomes through the follow-up period will occur with hierarchical mixed models specified for dichotomous or continuous outcomes. To use the mixed effect modeling analysis in assessing intervention effect, an interaction term (intervention group by time) will be included together with other covariates (e.g., age, ethnicity, chronic pain, anxiety, trauma history, utilization of psychiatric or medical services). A significant beta coefficient of the interaction term at $p < .05$ level will be used as evidence supporting the intervention effect. Analysis of change scores can analyze variables that cannot be normalized.

The Primary Aim 1 is to assess the efficacy of OARS+CM in promoting Suboxone treatment initiation.

The primary outcomes will be the proportion of participants who schedule a Suboxone treatment intake visit, and the proportion of participants who complete the Suboxone intake visit to start outpatient treatment. These outcomes are usually non-normally distributed and will be analyzed accordingly. We will assess the effect of the intervention using generalized linear mixed model, controlling for the dependence of repeated measures and the clustering effects.

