Aim 3 is to evaluate costs. Economic evaluation of the CM intervention is highly relevant to considerations of implementation and will be informed by expert guidelines.¹⁵⁹ The primary hypothesis is that the incremental cost-effectiveness (cost per participant who does not have repeat OUD-related emergency acute care, measured at the end of treatment and the last follow-up) will be acceptable and support sustainability. The study will also determine the incremental cost of the CM intervention per OUD patient treated, to identify the budget impact of adoption on a large-scale basis if the intervention is efficacious. For analyses, we will determine the Incremental Cost Effectiveness Ratio (ICER) in dollars per repeat acute care visit averted. This ratio is the difference in cost incurred by the OARS+CM group divided by the difference in the proportion of participants without repeat acute care services over the short (intervention period) and long term (last follow-up). The statistical uncertainty of the incremental cost-effectiveness will be estimated by bootstrap analysis of trial data, a method that preserves the covariance between costs and outcomes.¹⁶⁰ A cost-effectiveness acceptability curve will be plotted with the proportion of replicates that are cost-effective at different threshold values of willingness to pay per successful quit participant.¹⁶¹ The p -value for the statistical test that the OARS+CM intervention is cost-effective will be found by determining the proportion of replicates that are above each threshold value. We will conduct a literature review of cost-effectiveness studies to identify likely threshold values of dollars per OUD person treated in general. Costs of activities that are solely for research purposes (weekly surveys, follow-ups) will be excluded. Also see the Commercialization Plan for our approach to cost-savings and cost-avoidance.

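### Aim 3 names no baseline adjustment for the cost-effectiveness ratio, although utilization is recorded at intake; adjusting would be a cheap gain in precision for an exploratory aim

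*SAP*

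**What the plan says.** **The ratio.** The SAP's Aim 3 paragraph states: "This ratio is the difference in cost incurred by the OARS+CM group divided by the difference in the proportion of participants" without repeat acute care, over the intervention period and to the last follow-up.

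**Its uncertainty.** "The statistical uncertainty of the incremental cost-effectiveness will be estimated by bootstrap analysis of trial data". The p-value for cost-effectiveness "will be found by determining the proportion of replicates that are above each threshold value". No covariate, regression step or baseline value appears in the paragraph.

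**What is collected.** The Phase 2 assessment table in protocol section 11 has a row "Healthcare Utilization", marked at intake and month 6, and a row "Mini-UAT, Service Utilization, TLFB", marked at intake and months 1, 3 and 6.

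**Design.** Protocol section 25: "102 patients will be enrolled and randomized into OARS+CM (n=51), or TAU with MyMAT (n=51". Protocol section 5 describes an urn procedure "stratifying on 1) other (than opioid) substance use disorder no/yes, 2) gender/sex, 3) race/ethnicity". Prior utilization is not among these factors.

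**Covariates elsewhere.** The SAP's Phase 2 RCT paragraph gives examples of covariates for the group-by-time mixed models that include "trauma history, utilization of psychiatric or medical services". The same paragraph has a general rule: variables that differ significantly between arms at baseline, or that matter on theoretical grounds, enter multivariate analyses where appropriate. Its examples are pain and other substance use disorder.

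**Status.** Protocol section 4 calls the Aim 3 data exploratory. The SAP nevertheless gives Aim 3 a primary hypothesis and a p-value.

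**The concern.** Past acute care use is a plausible predictor of repeat acute care and, if cost includes later healthcare, of cost as well. The SAP treats utilization as worth adjusting for in its mixed models, but does not name it in the one analysis whose outcome is itself utilization.

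With 51 per arm and no balancing on this factor, one arm can by chance receive more prior heavy users. An unadjusted ratio carries that difference into the realized estimate. Bootstrap replicates centre on the observed data, so the acceptability curve moves with it. A baseline measure that could remove much of the shift and narrow the interval is scheduled for collection but has no stated use here. If the choice between an adjusted and an unadjusted ratio is left until the data are seen, two analysts could follow this SAP and report different ratios.

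**Working it through.** The SAP gives no power, cost SD, event rate or correlation for Aim 3, so there is no Aim 3 figure to reproduce. Its only power statement concerns intake completion and does not bear on this point.

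**1. Size of chance imbalance** (input from the protocol: 51 per arm).
- SD of the between-arm difference in a standardised baseline variable = sqrt(2/51) = 0.198.
- P(difference above 0.2 SD in either direction) = 2 × [1 − Φ(0.2/0.198)] = 0.31.
- P(difference above 0.3 SD in either direction) = 2 × [1 − Φ(0.3/0.198)] = 0.13.
- A baseline test at p < .05 needs about 1.96 × 0.198 = 0.39 SD. A 0.3 SD imbalance would therefore not trigger the SAP's significance-based covariate rule.

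**2. The same in terms of heavy users** (prevalence assumed). The SD of the difference in proportions is sqrt(2p(1 − p)/51). Exact binomial probabilities of a gap of at least 10 points in either direction:

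| Assumed prevalence | SD of difference (points) | P(gap ≥ 10 points) |
|---|---|---|
| 10% | 5.9 | 7% |
| 20% | 7.9 | 17% |
| 30% | 9.1 | 23% |
| 40% | 9.7 | 27% |

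Suppose heavy users have a repeat-visit risk 20 to 40 points higher, at 20% to 30% prevalence. A 1-SD imbalance then moves the denominator by 1.6 points (0.20 × 7.9) to 3.6 points (0.40 × 9.1).

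**3. Precision gain** (correlation assumed). Simulation with 51 per arm, log-normal cost and a yes/no event at 50%. Power after adjustment, starting from an assumed 80%, is Φ((1.96 + 0.84)/sqrt(V) − 1.96), where V is the ratio of adjusted to unadjusted variance.

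| Latent correlation | V, cost | V, proportion | Power |
|---|---|---|---|
| 0.3 | 0.96 | 0.96 | 82% |
| 0.5 | 0.85 | 0.85 | 86% |
| 0.7 | 0.73 | 0.71 | 91% |

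The textbook factor 1 − ρ² would give V = 0.91 at 0.3 and 0.75 at 0.5. It overstates the gain here because cost is skewed and the event is binary.

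**4. Effect on the realized result** (all inputs assumed). 8,000 simulated trials: 25% heavy users, repeat-visit risk 70% against 35%, mean cost $14,000 against $4,000, true effect 10 points, true cost difference $600, threshold $20,000 per participant. The last column is the average share of replicates judged cost-effective, by normal approximation, in the unadjusted analysis.

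| Trials | Effect, raw / adjusted (points) | Cost difference, raw / adjusted | Share, raw |
|---|---|---|---|
| All | 9.8 / 9.9 | $582 / $571 | 0.64 |
| OARS+CM has ≥ 10 points more heavy users (836) | 4.7 / 9.9 | $2,019 / $523 | 0.39 |
| OARS+CM has ≥ 10 points fewer (829) | 14.5 / 9.3 | −$856 / $613 | 0.84 |
| Gap under 3 points (2,178) | 9.8 / 9.7 | $568 / $570 | 0.65 |

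The two imbalanced rows are (836 + 829)/8,000 = 21% of trials. Across all trials the SD of net benefit falls from $2,779 to $2,405, which is 13% in SD or 1 − (2,405/2,779)² = 25% in variance. Coverage of the unadjusted 95% interval was 94.7%.

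**The case against.** **The unadjusted analysis is not wrong.** A reader might infer from the imbalanced rows above that the ratio is biased or that its bootstrap p-value is invalid for want of adjustment. The documents do not support that. Participants are randomized, so both differences are unbiased on average (9.8 points against a true 10), and the interval width already allows for chance imbalance (94.7% coverage). The contrast of 0.39 with 0.84 comes from selecting imbalanced trials under assumed inputs. This objection stands, and it limits the point to precision and to the estimate from the one trial that is run.

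**Silence is not a choice.** The Aim 3 sentence says what is divided by what, not how each difference is estimated, and an adjusted difference would fit it. The general covariate rule could be stretched to Aim 3, and the paragraph defers to external guidelines not reproduced here. It is therefore too strong to say that the SAP has chosen, or requires, an unadjusted ratio. What remains is that nothing links the covariate wording to Aim 3, so adjustment is left to the analyst.

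**The numerator may not be affected.** The scope of cost is not defined. If it covers only delivery of the contingency management programme, prior use enters mainly through the denominator. This stands.

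**The baseline item may not match the outcome.** The table shows row labels only. The outcome is repeat OUD-related acute care, and neither the content nor the look-back of the intake item is given. This stands and bears on the fix.

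**Other matters come first.** The paragraph describes its unit of effect in different ways: visits averted, participants without a repeat visit, and successful quits. That needs settling before any adjustment. With 51 per arm, a skewed baseline count could also give a few heavy users leverage in a regression. Both are fair.

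**Conclusion.** The point holds as a cheap improvement of modest weight. Aim 3 names no covariate for either difference or for the bootstrap, while utilization is recorded at intake and not balanced by the urn. The loss is efficiency, plus exposure of the realized ratio and acceptability curve to an imbalance that the trial will have measured.

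The imbalance figures (SD about 0.20, 13% chance of more than 0.3 SD) follow from the sample size alone, by normal approximation. The gain does not. It rests on an assumed correlation between intake use and outcome, and the power figures also on an assumed 80% start. At a correlation of 0.3 the benefit is small: a variance reduction of 4%, or about 2 points of power. At 0.5 it is 15%, or about 6 points. At 0.7 it is 27% to 29%. If cost means programme delivery only, the gain is mainly in the denominator. The exploratory status of Aim 3 keeps the priority low, although the stated hypothesis and p-value make it worth fixing the analysis in advance.

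**What to change.** Amend the SAP's Aim 3 paragraph as follows.

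1. Define the scope of cost and the unit of the denominator.
2. Name intake healthcare utilization as the baseline covariate, with one look-back period for all participants and a pre-specified form, such as a log or capped count, to limit leverage from a few heavy users.
3. Resample whole participants, so that the covariance between cost and outcome is preserved. Within each replicate, estimate the cost difference by regression on arm plus the covariate, and the difference in proportion without repeat acute care as a standardised risk difference from a model with the same terms.
4. Build the ratio and the acceptability curve from these adjusted differences.
5. Report the unadjusted ratio and curve as a sensitivity analysis.

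The cost is SAP wording and a few lines of code, with no new visits, patients or data items, provided the intake item supports a common look-back. The downside is one more modelling step per replicate and one functional-form choice to settle before the data are seen.

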Group A: TAU with MyMAT. For TAU participants, the usual care provided to individuals with OUD at the UMass University and Memorial hospitals will be provided. This typically consists of (1) medical stabilization and treatment, as needed; (2) brief counseling and referral to treatment by a social worker or other behavioral health provider, which includes providing a tailored referral list; and (3) when the patient is interested and treatment facility available, a "warm handoff" comprised of contact with the outpatient provider and transportation directly to the facility or a scheduled intake appointment within 48 hours, when feasible. TAU participants will also receive MyMAT, a mobile application with opioid treatment educational content, as an attention control measure against OARS+CM.

Group B: OARS+CM. Participants assigned to OARS+CM will receive the same treatment as in the TAU condition but with the enhancement of the CM features, described in detail in Section C.2.1, Proof-of-concept testing for usability section.

Table 1: Eligibility criteria						
Inclusion	Exclusion					
→ >= 18 years old	 Persistent altered mental status (not alert, not oriented, psychotic). 					
◆ Presenting for acute care at UMass University and Memorial hospitals, including EDs, inpatient medical units, inpatient behavioral health units, or community acute care partners for opioid addiction related health complaints, including opioid overdose, opioid related medical consequences, opioid intoxication or withdrawal syndromes, and/or seeking help for OUD	Patient declines referral to UMass Bridging MAT Clinic, to CleanSlate Addiction Treatment Center, to SaVida Health, to Eleanor Health, or to Spectrum Health Systems for MOUD.					
 Presence of a current DSM-V opioid use disorder (OUD), mild to severe 	 Not interested or willing to participate in MOUD treatment 					
 Medically appropriate for outpatient MOUD treatment, as judged by the 	 Unwilling to use the OARS+CM app (if assigned) 					
treating clinician and behavioral health consultant or toxicologist working with the patient clinically	 Does not have access to their own smartphone with at least iOS 7.1 or Android 4.2, the minimal technology required to run the app, or not willing to access clinic- dedicated computer to access the program 					

	Currently a UMMS student			
 Treatment provider of patient who 	 Prisoner or currently in state custody or 			

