- 4. Participants will receive a welcome call at 1-week post-enrollment. This call will welcome participants to the study and provide an opportunity to answer any questions they may have about participation as well as ensure they are not having any issues with study mobile applications. This call will take about 5 minutes.
- 5. They will complete 3 follow-up telephone calls to find out how they are doing. The calls will focus on their substance use, especially opioid use, treatment engagement, healthcare visits, health, and well-being. These calls will take about 20 30 minutes to complete. The calls will occur at 1, 3, and 6 months after the enrollment date.
- 6. The researchers will review the participants' healthcare records, including the Massachusetts Prescription Monitoring Program's EHR-integrated tool MassPAT that provides information on participant's prescriptions for MOUD through the 6 months after enrollment. We will review the

healthcare record for all participants and will only be viewing the MassPAT record for participants who do not have urine toxicity results at their outpatient MOUD provider at the 1, 3, and 6-month follow up time points. MassPAT will be used to determine if a participant is still engaging in treatment during these follow-up time points if the participant cannot be reached for their follow-up interviews or if they have stopped attending appointments at their study clinic site and have not requested to leave the study.

- 7. We will be seeking to collect information from medical providers or records outside of the UMMS system (a substance use treatment provider in the community that doesn't have a UMMS connection) and will require a signature on a Release of Medical Information with designated treatment facilities identified
- 8. The researchers will review publicly available databases, like the participants' state's vital statistics registry (a document created by the state that tracks important health indicators, like births, deaths, and cause of death). See grant: "RESEARCH STRATEGY" (p.8-13) for details.

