Statistical Design and Power

Data analyses will proceed with the intent-to-treat sample. Initial analyses will compare groups on baseline and demographic variables using chi-square test (for categorical variables) and analysis of variance (for continuous variables). Variables that significantly differ between groups or are theoretically important, such as pain and other (non-opioid) substance use disorder will be used as covariates in multivariate analysis, when appropriate. For end-of-treatment outcomes, analysis will compare groups via chi-square, Kruskal-Wallis test, and analysis of variance (ANOVA) or analysis of covariance (ANCOVA) tests, as appropriate. Evaluation of changes in outcomes through the follow-up period will occur with hierarchical mixed models specified for dichotomous or continuous outcomes (PROC MIXED and PROC GLIMMIX SAS procedures). These analyses allow for intra-subject serial correlation, unequal variance and covariance structures, and unequally spaced assessment intervals. They also account for missing data by using all available data and maximum likelihood estimation of parameters. To use the mixed effect modeling analysis in assessing intervention effect, an interaction term (intervention group by time) will be included together with other covariates (e.g., age, ethnicity, chronic pain, anxiety, trauma history, utilization of psychiatric or medical services). A significant beta coefficient of the interaction term at $p < .05$ level will be used as evidence supporting the intervention effect. Analysis of change scores can analyze variables that cannot be normalized. For all analyses, effect sizes will be estimated, with parametric and non-parametric statistics as appropriate; effect sizes for effects by sex will be estimated. Statistical significance will be at $p < .05$ and analyses will occur via IBM® SPSS® Statistics V21 and SAS 9.4 statistical software package (SAS Institute Inc, Cary, NC).

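### Aim 3 does not say how deaths enter the proportion without repeat acute care; read literally, a death with no earlier repeat visit counts as a success

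*SAP*

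**What the plan says.** The SAP's Aim 3 paragraph gives the ICER denominator as "the difference in the proportion of participants without repeat acute care services over the short (intervention period) and long term (last follow-up". The hypothesis in the same paragraph uses a closely related unit: "cost per participant who does not have repeat OUD-related emergency acute care, measured at the end of treatment and the last follow-up". Neither definition refers to survival.

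Under Phase 2, RCT, the SAP says that the analysis "will proceed with the intent-to-treat sample", so a participant who dies stays in the arm to which he or she was randomized. Death is not mentioned anywhere in the SAP: there is no composite, competing-event, censoring or exclusion rule.

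The protocol plans to learn of deaths. In section 11, Phase 2, step 8, staff will review the state's "vital statistics registry (a document created by the state that tracks important health indicators, like births, deaths, and cause of death". Table 1 in section 6 admits patients with opioid-related presentations, "including opioid overdose, opioid related medical consequences, opioid intoxication or withdrawal syndromes". Section 25 sets the arm sizes: "102 patients will be enrolled and randomized into OARS+CM (n=51), or TAU with MyMAT (n=51".

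**The concern.** Deaths within six months are foreseeable in a population that includes people enrolled after an overdose. Section 11 of the protocol has healthcare records reviewed for every participant and schedules healthcare utilization at intake and Month 6. In such records, the absence of visits after a death outside hospital looks the same as the absence of any need for care. Unless a rule links the registry data to the endpoint, such a person is classed as having had no repeat care, which is the favorable category.

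The effect measure would then give credit for the worst outcome. Costs may also stop accruing at death, and the plan has no rule for that either. The planned bootstrap resamples whatever coding is used, so it cannot correct the classification. If the question is left until the data are in, the choice of coding could be made with the results in view.

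**Working it through.** The documents give no ICER, repeat-care rate, cost difference or death rate, so there is no stated figure to reproduce. What can be shown is how sensitive the ratio is to the coding of deaths.

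**Inputs**
- From the documents: 51 participants per arm (protocol section 25), and ICER = cost difference / (proportion without repeat care on OARS+CM minus the same proportion on TAU with MyMAT) (SAP, Aim 3).
- Assumed: the observed difference D with deaths coded literally (20, 10 and 5 points), the event counts below, and a cost difference of $500, held fixed.

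**Effect of one death.** Rescoring one death from success to failure moves that arm's proportion by 1/51 = 1.96 points.

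**Effect on the ratio.** Let k be the number of such deaths on OARS+CM minus the number on TAU with MyMAT. Rescored ICER / literal ICER = D / (D - 1.96k), with D in points.

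| Assumed D | k = +1 (one more on OARS+CM) | k = -1 (one more on TAU) |
|---|---|---|
| 20 points | 20/18.04 = 1.109 (+11%) | 20/21.96 = 0.911 (-9%) |
| 10 points | 10/8.04 = 1.244 (+24%) | 10/11.96 = 0.836 (-16%) |
| 5 points | 5/3.039 = 1.645 (+65%) | 5/6.961 = 0.718 (-28%) |

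With k = 0 the denominator does not change, however many such deaths occur.

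**Worked counts, $500 cost difference (assumed)**
- 36/51 on OARS+CM against 31/51 on TAU: the difference is 5/51 = 9.8 points and the ICER is 500/(5/51) = $5,100. Two more such deaths on OARS+CM give 3/51 = 5.9 points and $8,500. Two more on TAU give 7/51 = 13.7 points and $3,643.
- 33/51 against 31/51: the difference is 2/51 = 3.9 points and the ICER is $12,750. Two more such deaths on OARS+CM give a difference of zero and an undefined ICER. Two more on TAU give 4/51 = 7.8 points and $6,375.

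**Sign reversal.** A positive D reverses only if 1.96k exceeds D. For k of 1 or 2, D must be below 2/51 = 3.9 points. At D = 10 points, five net deaths (9.8 points) are not enough and six are needed (6/51 = 11.8 points).

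**Scale against sampling error.** With an assumed proportion near 65% in both arms, the standard error of the difference is sqrt(2 x 0.65 x 0.35 / 51) = 9.4 points. One death is therefore about 1.96/9.4 = 0.2 of a standard error.

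**The case against.** The strongest reply is that the plan is silent on deaths and does not say that they are successes. A reader might infer that it does, but no sentence says so, and an analyst could code deaths as failures, exclude them or treat them as missing. That is correct. What remains is that the definition as written, applied to record-based utilization in an intent-to-treat sample, leads to the favorable coding unless someone steps in.

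Three other stronger readings are tempting, and the documents do not support them.

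- *Every death counts as a success.* A participant with a repeat visit before death, or whose fatal event was itself treated in acute care, already counts as having had repeat care.
- *One or two deaths would overturn the result.* This needs an imbalance between arms and an observed difference under about 3.9 points. A difference that small is already well inside the sampling error shown above.
- *The same defect affects the mixed models and Aim 2.* The SAP's missing-data sentence, "They also account for missing data by using all available data and maximum likelihood estimation of parameters", describes the mixed models, does not mention death and does not govern the ICER. Abstinence in Aim 2 is built from negative urine samples together with self-reported non-use. A deceased participant can supply neither, so no defect is shown there.

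Two further objections stand as limits. Counting death from any cause as a failure makes the effect a composite, which no longer matches a cost per visit averted; competing-event methods would also be defensible. In addition, section 10 of the protocol refers to grant pages for the endpoints, and the registry step in section 11 also refers to the grant. Those pages were not available and could contain a rule.

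**Conclusion.** The gap is real and narrow. Aim 3 does not say how deaths enter its effect measure, and the literal definition classes a death without earlier or terminal acute care as a success. The size is 2.0 points per such death in an arm of 51. At an assumed 10-point difference, a net imbalance of one changes the ICER by about -16% or +24%. The direction depends on which arm has more such deaths, and balanced deaths leave the denominator unchanged.

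These percentages hold the cost difference fixed. The SAP excludes research-only costs but does not list the cost components, so the effect of death on the numerator cannot be sized. The number of deaths, the repeat-care rates and the $500 are assumptions.

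The severity is minor. Section 4 of the protocol describes the Aim 3 cost data as exploratory, although the SAP attaches a primary hypothesis and a p-value to them. The primary outcomes, scheduling and completing the treatment intake, are not affected.

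**What to change.** In the SAP's Aim 3 paragraph:

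1. Define the effect as the proportion alive and without repeat OUD-related acute care, at the end of treatment and at the last follow-up. Death from any cause, identified from the vital statistics review already planned, counts as not a success.
2. State how costs are handled after death.
3. Report the current definition, without the survival condition, as a sensitivity analysis.
4. Label the ratio as cost per additional participant alive without repeat OUD-related acute care, because the effect is now a composite.

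If the grant pages already contain a rule for deaths, copy it into the SAP. The cost is a few sentences and no new data collection. The small downside is that the ratio can no longer be read as dollars per repeat visit averted. No change to the mixed models or to Aim 2 is needed on this ground.
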